## **INFORMED CONSENT**

- Informed consent will be an agreement between the individual investigator and each subject, having the capacity to understand and make an informed decision. Consent will be obtained prior to each potential subject's participation in this clinical study.
- Each subject participating in this clinical study will be made aware of the fact that his or her participation involves research and the intent of the research, the expected duration of his or her participation and a description of the procedures that will be followed.
- Each subject will be made aware of the reasonably expected benefits he or she might receive, as well as any risks or potential discomfort that are involved.
- Each subject will also be made aware of alternative treatments available to him or her.
- Each subject will be made aware that his or her records will remain confidential, but that the FDA and the IRB has the right to inspect his or her records.
- Each subject will be told that his or her participation in the clinical study is voluntary, without force or influence from the investigator or sponsor.
- Each subject will be given the name and method of contacting the appropriate person(s) to answer his or her questions about the research and in the event of a research-related injury.

The informed consent form that will be used to collect the data from each subject in this clinical study can be found in **Appendix B**.

## **CASE REPORT FORMS**

The case report forms that will be used to collect the data from each subject in this clinical study can be found in **Appendix C**.

## **APPENDIX A**

### **LETTER OF APPLICATION FOR NON-SIGNIFICANT RISK (NSR) DETERMINATION**

**ERCHONIA CORPORATION**  
**LETTER OF APPLICATION FOR NONSIGNIFICANT RISK DETERMINATION**  
**FOR THE ERCHONIA® EVRL LASER DEVICE**  
**FOR REDUCING NECK AND SHOULDER PAIN**  
**CLINICAL STUDY V1.0 03.21.18**

**NAME OF THE DEVICE:** Erchonia® EVRL

**INVESTIGATIONAL INDICATION:** The purpose of this clinical study is to determine the effectiveness of the Erchonia® EVRL (manufactured by Erchonia Corporation (the Company)), when both the red and blue diodes are activated simultaneously, in providing temporary relief of minor chronic neck and shoulder pain of musculoskeletal origin.

The purpose of this clinical study Erchonia® EVRL Laser being evaluated in this clinical study for adjunctive use in providing temporary relief of minor chronic neck and shoulder pain of musculoskeletal origin has received FDA clearance under **K050672** for the following indication:

**REGULATORY BACKGROUND**

The Erchonia® EVRL Laser being evaluated in this clinical study for adjunctive use in providing temporary relief of minor chronic neck and shoulder pain of musculoskeletal origin has received FDA clearance under **K050672** for the following indication:

The Erchonia EVRL Laser is generally indicated:

- a. while using the red diode, for adjunctive use in providing temporary relief of minor chronic neck and shoulder pain of musculoskeletal origin, and
- b. while using the blue diode, to treat dermatological conditions, and specifically indicated to treat moderate inflammatory Acne Vulgaris.

However, its application in this clinical trial is experimental, as it is the goal of the current study to demonstrate non-inferiority in efficacy of the Erchonia® EVRL when used in simultaneous dual diode mode (both the red (640 nm) and violet (405 nm) diodes activated simultaneously) compared to its use with the red diode only activated.

**DEVICE DESCRIPTION & DETAILS**

The Erchonia® EVRL (Model# EVRL) used in this study is a hand held low level laser that uses two semi-conductor diodes; a 640 nanometer (visible red light) and a 405 nanometer (visible violet light), each emitting its wavelength with a tolerance of  $\pm 10$  nanometer. The lasers are powered by an internal battery that is recharged using a separate inductive charging base powered by an external class II medical power supply. This configuration offers portability as well as consistency of power. The Erchonia® EVRL is a variable hertz device. The variable hertz feature of the Erchonia® EVRL is a pulsed wave, defined as containing a selected series of breaks, variances that are preprogrammed.

The internal battery powers the two specially created and patented electronic diodes with an output of 7.5mW red  $\pm 1$  mW and <5mW violet laser.

The device contains software that is embedded in a RAM chip on the PCB. This data includes the touch screen images (GUI) and the command prompts that activate the screen icons; work in

conjunction with the component platform to ensure the device operates as intended. The exterior materials consist of 6061 T6 AL and Copolymer Acetal with powder coating finish.

The Erchonia® EVRL has the following specifications:

#### **Device**

- Weight: Laser-.95lbs / .42kgs. Charger Base-.55lbs / .42kgs
- Full Color TFT Touch Screen Module
- Machined billet aluminum enclosure
- Dimensions: Laser-Length-6.9" (17.52cm) Width-3.10" (7.87cm) Depth-.76" (1.93cm), Charger Base- Length-5.7" (14.47cm) Width-3.5" (8.88cm) Depth-1.65" (4.19cm)

#### **Laser**

- 2 electronic diodes, with patented optics
- Output: 640 nm 7.5mW  $\pm$  1mW (red)
- Output: 405 nm<5mW (violet)
- Wavelengths: 640 nm & 405nm +/- 10nm
- Duty Cycle: 50%

#### **Power**

- Battery: Lithium-ion Polymer 3.7V, 1500mAh, 5.6w

#### **Inductive Charging Base**

- 1.5A 12V

#### **External Power Supply**

- Model: ER-E-00182
- 100-240Vac, 50-60Hz, 0.5A; 12Vdc 1.5A

#### **Dosage calculations for the Erchonia® EVRL**

Total energy per diode:

- (diode output means) mW / 1000 (converting mW to W) \* (time in seconds)  $\div$  2 (50% duty cycle) = (total energy per diode per minute)
- 640 nm diode (red): 7.5 / 1000 \* 60  $\div$  2 = .225J
- 405 nm diode (violet): 4.5 / 1000 \* 60  $\div$  2 = .135J
- Total device diodes energy per minute: .36J
- The Erchonia® EVRL used in this study is shown in Figure 1 below.

Figure 1

The following diagram identifies each component of the device and a complete description of the component follows.

Figure 2

#### **#1 POWER BUTTON (ON/OFF)**

The Power Button allows you to turn the device ON “|” or OFF “O”. To turn the device ON, press and Hold this button, after approximately 3 seconds the green (#2 Power On Light) turns on. To turn off the device it is recommended to use the “**Powering Down**” method, explained in the **Operation Section** of the manual. In the unlikely event that your device stops responding to touches, by pressing and holding the power button for 15 seconds will force shut down the device. This is only recommended if the device cannot be turned off from the “**Powering Down**” method.

#### **#2 LASERS ON LIGHT**

The “Lasers On” light is an LED indicator that will light up when the Lasers are ON and turn off when the lasers are OFF.

#### **#3 POWER ON LIGHT**

The “Power On” light is an LED indicator that will display a constant green light when the device is powered on and turn off only when the device is OFF.

#### **#4 TOUCH SCREEN**

The touch screen functions as a display screen and an input panel, providing information and a means to operate the device by touching the appropriate icon.

### **#5 PIVOTING LASER MOUNT**

The Pivoting Laser Mount allows you to adjust the laser angle (up to 20° each direction) based on your preference.

### **#6 LASER DIODES**

The Lasers consist of two electronic laser diodes, with patented optics. These laser diodes when activated by the internal power source generate laser energy thereby emitting on one side a red beam and the other side a violet beam. This is a specially designed and patented device created to ensure the laser beam is focused and directed for the most optimal use. The device can be programmed with up to 4 defined Hz frequencies (two for each diode).

### **CHARGER BASE**

Directions to set Device on Charger Base

[figure not shown]

Figure 3

### **POWER SUPPLY**

Figure 4

### **#1 INDUCTIVE CHARGER BASE**

The Inductive Charger Base is a custom based system specifically designed to charge the laser device. It is an inductive charging system that charges the device wirelessly. The Charger Base must be plugged into the power supply and the power supply must be plugged into a wall socket for Charger Base to receive power. Once powered up, the Laser device is placed on Charger Base with the touch screen facing up and Laser diodes facing away from Charger Base LED lights.

### **#2 CHARGER BASE POWER LIGHT**

The Charger Base “Power” Light is the power indicator LED that will light up when the energized Power Supply connector is plugged into the Inductive Charger Base.

### **#3 DOCKED LIGHT**

The “Docked” light is an indicator LED that will light up to indicate the device is correctly docked in the inductive charger base. The LED will flash ON and OFF when correctly in place and turn off when removed from the inductive charger base.

### **#4 CHARGER BASE CONNECTOR PORT**

The Charger Base Connector Port is the location to plug the Power Supply Connector in to supply power to the inductive charger base.

### **#5 POWER SUPPLY CONNECTOR**

The Power Supply Connector plugs into the Inductive Charger Base Connector Port to provide power to charger base.

## DEVICE SAFETY

### RISK AND PREVENTION OF EYE INJURY

The Erchonia® EVRL is classified by the FDA/IEC as a Class 2 laser device. This designation represents a current standard for use in order to ensure the safety of the subject. A Class 2 laser is determined to have a chronic viewing hazard. Pointing the laser beam directly into the eye and maintaining it there for an extended period of time could prove to be damaging.

To ensure there is no possible instance of residual effect, eye protection is implemented for the subject receiving the laser procedure administrations.

A pair of safety glasses is provided for use during all procedure applications. These safety glasses are Kentek PN: C22-KMT-6101. The safety glasses, sufficiently and effectively block the laser light spectrum at OD 2+ @ 635nm, OD 0.75 @ 405nm VLT 60%.

- Height: 40 mm
- Width: 145 mm
- Length: 165 mm

### FOOD AND DRUG ADMINISTRATION (FDA) DETERMINATION OF NON-SIGNIFICANT RISK (NSR) STATUS

(i) Regulatory Clearances: The Food and Drug Administration (FDA) has determined the family of Erchonia® low level laser devices, including those employing 635 nm red diodes and 405 nm blue/violet diodes, to be non-significant risk (NSR) through numerous **510(k) clearances**, including several for pain relief indications, as follows.

1. **K132940**: *Erchonia® Allay™*: is indicated as an adjunct to reducing chronic heel pain arising from plantar fasciitis.
2. **K072206**: *Erchonia® EML Laser*: is indicated for the temporary reduction in post-surgery pain at 24 hours after surgery following bilateral breast augmentation surgery.
3. **K050672**: *Erchonia® EVRL Laser*: The Erchonia EVRL Laser is generally indicated:
  - a. while using the red diode, for adjunctive use in providing temporary relief of minor chronic neck and shoulder pain of musculoskeletal origin, and
  - b. while using the blue diode, to treat dermatological conditions, and specifically indicated to treat moderate inflammatory Acne Vulgaris.
4. **K041139**: *Erchonia® EML Laser*: is indicated as an adjunct to liposuction procedures of the thighs, hips and stomach for reduction of pain associated with the recovery process.

5. **K100509 & K130741:** *Erchonia® THL 1 Laser & Erchonia® PL5000*: is indicated for adjunctive use in providing temporary relief of minor chronic neck and shoulder pain of musculoskeletal origin.
6. **K130996:** *Erchonia® XLR8™*: The Erchonia XLR8™ is indicated for the following three indications:
  - a. adjunctive use in providing temporary relief of minor chronic neck and shoulder pain of musculoskeletal origin
  - b. as an adjunct to liposuction procedures of the thighs, hips and stomach for reduction of pain associated with the recovery process
  - c. temporary reduction in post-surgery pain at 24 hours after surgery following bilateral breast augmentation surgery
7. **K142042:** *Erchonia® SHL Laser*: is indicated for use as a non-invasive dermatological aesthetic treatment for reduction of circumference of hips, waist and upper abdomen when applied to individuals with a Body Mass Index (BMI) between 30 kg/m^2 and 40 kg/m^2.
8. **K130922:** *Erchonia® Verju Laser System with Massager*: is indicated for use as a non-invasive dermatological aesthetic treatment as an adjunct for individuals intending to undergo liposuction procedures for the reduction of circumference of hips, waist and thighs. The Massager component is indicated for the temporary reduction in the appearance of cellulite.
9. **K123237 & K133718:** *Erchonia® Zerona™ 2.0 Laser & Zerona®-Z6*: is indicated for use as a non-invasive dermatological aesthetic treatment as an adjunct for individuals intending to undergo liposuction procedures for the reduction of circumference of hips, waist, and thighs.
10. **K121695 & K082609:** *Erchonia® ML Scanner (MLS) & Erchonia® Zerona*: is indicated for use as a non-invasive dermatological aesthetic treatment as an adjunct for individuals intending to undergo liposuction procedures for the reduction of circumference of hips, waist, and thighs.
11. **K21690 & K120257:** *Erchonia® MLS, Zerona, Zerona-AD*: is indicated for use as a non-invasive dermatological aesthetic treatment as an adjunct for individuals intending to undergo liposuction procedures for the reduction of circumference of the upper arms.
12. **K101430:** *MLS-AC Derma Scanner™*: is indicated while using the red diodes for adjunctive use in providing temporary relief of minor chronic neck and shoulder pain of musculoskeletal origin, and while using the blue diode, to treat moderate inflammatory Acne Vulgaris.
13. **K082609:** *Erchonia® ML Scanner (MLS)*: is indicated for use as a non-invasive dermatological aesthetic treatment for the reduction of circumference of hips, waist and thighs.

(iii) **Pre-IDE Reviews:** FDA has previously reviewed numerous clinical study protocols employing various Erchonia® Corporation low level laser devices, including all of the clinical studies conducted in support of the above 510(k) clearances and those employing 635 nm red diodes. For all of the FDA's pre-IDE reviews of Erchonia low level laser clinical study protocols, there was concurrence from FDA that the clinical study protocols and application of the Erchonia laser devices therein were considered non-significant risk (NSR).

**INSTITUTIONAL REVIEW BOARD (IRB) DETERMINATION OF NON-SIGNIFICANT RISK (NSR) STATUS**

Erchonia® Corporation low level laser devices have been determined to be non-significant risk (NSR) when applied in various clinical studies through several IRBs, including those involving application of 635 nm red diode energy and 405 nm blue/violet diode energy, and application for pain reduction indications, as follows:

- Western Institutional Review Board (WIRB®) has previously determined Erchonia low level laser devices to be non-significant risk (NSR) when applied in the following clinical studies:
  1. **WIRB PRO NUM: 20121548:** Erchonia® MLS: A double-blind, placebo-controlled randomized evaluation of the effect of the Erchonia® ML Scanner (MLS) laser on reducing pain associated with degenerative arthritis (osteoarthritis) of the midfoot clinical study protocol
  2. **WIRB PRO NUM: 20120787:** Erchonia® MLS: A double-blind, placebo-controlled randomized evaluation of the effect of the Erchonia® ML Scanner (MLS) on low back pain clinical study protocol
  3. **WIRB PRO NUM: 20111793:** Erchonia® MLS: A double-blind, placebo-controlled randomized evaluation of the effect of the Erchonia® ML Scanner (MLS) laser on chronic heel pain clinical study protocol
  4. **WIRB PRO NUM: 20110331:** Erchonia® MLS: An evaluation of the effectiveness of the Erchonia® ML Scanner (MLS) as a non-invasive dermatological aesthetic treatment for the reduction of circumference of the upper arms clinical study protocol
  5. **WIRB PRO NUM: 20120911:** Erchonia® MLS: A double-blind, placebo-controlled randomized evaluation of the effect of the Erchonia® ML Scanner (MLS) on body contouring of the waist, hips and thighs five-day treatment protocol clinical study protocol
  6. **WIRB PRO NUM: 20110758:** Erchonia® MLS: A pilot evaluation of the effect of the Erchonia® ML Scanner (MLS) laser device on enhancing body weight loss, fat loss and circumference reduction of the waist, hips and thighs clinical study protocol
  7. **WIRB PRO NUM: 20121330:** Erchonia LUNULA™: An Evaluation of the Effect of the Erchonia LUNULA™ on Treating Toenail Onychomycosis Clinical Study Protocol; Version 6.0 August 7, 2012
  8. **WIRB PRO NUM: 20110461:** Erchonia FX-405™: An Evaluation of the Effect of the Erchonia FX-405™ on Treating Toenail Onychomycosis Clinical Study Protocol; Version 3.0 March 19, 2011
  9. **WIRB PRO NUM: 20120489:** Erchonia® MLS: A double-blind, placebo-controlled randomized evaluation of the effect of the Erchonia® ML Scanner (MLS) on lipid panel levels clinical study protocol
- Independent Review Consulting, Inc.'s/Ethical and Independent Review Services has previously determined Erchonia low level laser devices to be non-significant risk (NSR) when applied in the following clinical studies:

1. **IRC# 07150, NSR# DER-006:** Erchonia® MLS: A double blind, placebo-controlled randomized evaluation of the effect of the Erchonia® ML Scanner (MLS) on body contouring of the waist, hips and thighs clinical study protocol.
2. **IRC# 09120, NSR# DER-015:** Erchonia® MLS: A double-blind, placebo-controlled randomized evaluation of the effect of the Erchonia® ML Scanner (MLS) on reducing the appearance of cellulite clinical study protocol.
3. **IRC# 08167, NSR# DER-009:** Erchonia® MLS: A double blind, placebo-controlled randomized evaluation of the effect of the Erchonia® ML Scanner (MLS) on capsular contracture clinical study protocol.
4. **IRC# 09059, NSR# DER-010:** Erchonia® MLS: A double blind, placebo-controlled randomized evaluation of the effect of the Erchonia® ML Scanner (MLS) in combination with silicone sheets on cellulite pilot study protocol.

➤ Chesapeake Research Review, Inc. determined the Erchonia® ML Scanner (MLS) laser device to be a non-significant risk (NSR) device when applied in the following study:

- (i) **Pro. # 00006393:** Erchonia® MLS: A pilot evaluation of the effect of the Erchonia® ML Scanner (MLS) as applied to the abdomen on reducing visceral abdominal fat in patients with HIV-associated lipodystrophy.

#### OTHER POTENTIAL RISKS

Other potential risks and their mitigation include:

- (iv) Electric shock: operator risk only: mitigated through electrical safety testing.
- (v) Electromagnetic interference: mitigated through EMC/EMI testing.
- (vi) User error: mitigated through instructions for use documentation.

#### LABELING

The device used in this clinical study shall be labeled with the following statement:

"CAUTION – Investigational device. Limited by United States law to Investigational use."

➤ Do you contend that this device as used in this protocol is an NSR device?  
\_\_\_\_\_ Yes  No

➤ Has another IRB decided this device is SR?  
\_\_\_\_\_ Yes  No

➤ Does this type of device appear as SR on the FDA Information Sheet?  
\_\_\_\_\_ Yes  No

# **APPENDIX C**

# **CASE REPORT FORMS**

**ERCHONIA® EVRL NECK & SHOULDER PAIN CLINICAL STUDY****PRE-PROCEDURE ACTIVITIES: STUDY QUALIFICATION EVALUATION**Subject ID:  Investigator initials:  Date: **INCLUSION CRITERIA**

Mark each box below that applies:

	Study informed consent form signed
	18 years of age or older
	primary language is English
	Subject presents with one or more of: 
 
 chronic neck pain on the right side of the neck and/or the left side of the neck and/or the back of the neck; and/or
 
 chronic shoulder pain on the right shoulder and/or the left shoulder
 

**PHYSICAL EXAMINATION RESULTS RECORD****(i) INSPECTION FINDINGS**

	Finding	Location of Finding
	Knots (muscle spasms)	
	Tightness	
	Swelling	
	Osteophytes	
Additional relevant findings		

**(ii) PALPATION ASSESSMENT FINDINGS**

	Finding	Location of Finding
	Muscle tightness/knotting	
	Trigger points that worsen pain with palpation	
	Radiating pain upon trigger point palpation	
Additional relevant findings		

**(iii) RANGE OF MOTION ASSESSMENT**NECK ROM

ACTIVE NECK ROM	MEASUREMENT (degrees)	PAIN	WEAKNESS
Sagittal plane flexion		YES / NO	YES / NO
Sagittal plane extension		YES / NO	YES / NO
Frontal plane right lateral flexion		YES / NO	YES / NO
Frontal plane left lateral flexion		YES / NO	YES / NO
Transverse plane right rotation		YES / NO	YES / NO
Transverse plane left rotation		YES / NO	YES / NO

PASSIVE NECK ROM	MEASUREMENT (degrees)	PAIN	WEAKNESS
Sagittal plane flexion		YES / NO	YES / NO
Sagittal plane extension		YES / NO	YES / NO
Frontal plane right lateral flexion		YES / NO	YES / NO
Frontal plane left lateral flexion		YES / NO	YES / NO
Transverse plane right rotation		YES / NO	YES / NO
Transverse plane left rotation		YES / NO	YES / NO

MANUAL RESISTANCE NECK ROM	MEASUREMENT (degrees)	PAIN	WEAKNESS
Sagittal plane flexion		YES / NO	YES / NO
Sagittal plane extension		YES / NO	YES / NO
Frontal plane right lateral flexion		YES / NO	YES / NO
Frontal plane left lateral flexion		YES / NO	YES / NO
Transverse plane right rotation		YES / NO	YES / NO
Transverse plane left rotation		YES / NO	YES / NO

SHOULDER ROM

ACTIVE SHOULDER ROM	MEASUREMENT (degrees)	PAIN	WEAKNESS
Right abduction		YES / NO	YES / NO
Left abduction		YES / NO	YES / NO
Right adduction		YES / NO	YES / NO
Left adduction		YES / NO	YES / NO
Right extension		YES / NO	YES / NO
Left extension		YES / NO	YES / NO
Right flexion		YES / NO	YES / NO
Left flexion		YES / NO	YES / NO

PASSIVE SHOULDER ROM	MEASUREMENT (degrees)	PAIN	WEAKNESS
Right abduction		YES / NO	YES / NO
Left abduction		YES / NO	YES / NO
Right adduction		YES / NO	YES / NO
Left adduction		YES / NO	YES / NO
Right extension		YES / NO	YES / NO
Left extension		YES / NO	YES / NO
Right flexion		YES / NO	YES / NO
Left flexion		YES / NO	YES / NO

MANUAL RESISTANCE SHOULDER ROM	MEASUREMENT (degrees)	PAIN	WEAKNESS
Right abduction		YES / NO	YES / NO
Left abduction		YES / NO	YES / NO
Right adduction		YES / NO	YES / NO
Left adduction		YES / NO	YES / NO
Right extension		YES / NO	YES / NO
Left extension		YES / NO	YES / NO
Right flexion		YES / NO	YES / NO
Left flexion		YES / NO	YES / NO

 Subject is diagnosed with of one or more of the following (check each that applies) j 
 
 Osteoarthritis: Degenerative Joint Disorder (DJD)
 
 Chronic Muscle Spasms
 
 Cervical and Thoracic Spine Sprain Strain
 
 
j based on the following criteria specific to each condition:
 
A. Osteoarthritis: Degenerative Joint Disorder (DJD)
 
 
 Patient History: Previous trauma or infection to the area
 
 Medication Use History: Anti-inflammatory medications; either over-the-counter (e.g. Advil, Motrin, Aspirin); prescription medications (e.g. Celebrex, Vioxx)
 
 Previous Records Review: DJD indicated
 
 Physical Examination: Pain and pain with ROM evaluation; reduced ROM, particularly passive ROM motion; cracking/popping/creaking sound upon movement (ROM); possible joint swelling; possible bone spurs (osteophytes)
 
 
B. Chronic Muscle Spasms
 
 
 Patient History: Previous trauma; "frozen" shoulder and/or neck; history of restricted range of motion; pain relief through heat application and/or physical manipulations such as massage and physical therapy
 
 Medication Use History: Over-the-counter/prescription muscle relaxers and palliatives
 
 Previous Records Review: Lack of DJD indicated
 
 Physical Examination: Limited ROM; muscle tightness/knotting; tenderness and pain upon palpation; possible radiation pain upon palpation of tender spots (trigger points)
 
 
C. Cervical and Thoracic Spine Sprain Strain
 
 
 Patient History: Injury or pain initiated after motion or repetitive motion and exacerbated by motion; history of an old injury that can be exasperated acutely; pain and weakness on flexion; increased joint pain at the end range of motion.
 
 Medication Use History: OTC and/or prescription muscle relaxants or anti-inflammatory medications.
 
 Previous Records Review: Muscle or ligament injury indicated.
 
 Physical Examination: Pain that worsens with movement (active and/or passive ROM); reduced ROM; muscle weakness; stiffness; tenderness upon palpation; possible swelling.
 

 Neck/shoulder pain is chronic: symptoms have persisted for longer than the past 30 days

	
Degree of Pain Self-Rating on the 0-100 Visual Analog Scale (VAS) is 50 or greater
 
Please mark with an 'X' a single spot along the 0 to 100 line below that best shows how much pain you feel right now in your neck and/or shoulder, where '0' means 'no pain' and '100' means 'worst pain imaginable'. MARK ONLY ONE SPOT. DO NOT THINK OF OR WRITE IN A NUMBER.
 
  
 
VAS Rating: _____

	Subject is willing and able to refrain from consuming any over-the-counter and/or prescription medication(s) and/or herbal supplements intended for the relief of pain and/or inflammation, including muscle relaxants throughout the course of study participation
	Subject is willing and able to refrain from engaging in any non-study procedure therapies for the management of his or her neck/shoulder pain throughout the course of study participation, including conventional therapies such as physical therapy, occupational therapy and hot or cold packs, as well as alternative therapies such as chiropractic care and acupuncture

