- Physical Examination: Pain that worsens with movement (active and/or passive ROM); reduced ROM; muscle weakness; stiffness; tenderness upon palpation; possible swelling.

3. Pain is chronic: symptoms have persisted for longer than the past 30 days
4. Subject's self-reported Degree of Pain rating on the 0-100 VAS pain scale is 50 or greater
5. Subject is willing and able to refrain from consuming any over-the-counter and/or prescription medication(s) and/or herbal supplements intended for the relief of pain and/or inflammation, including muscle relaxants throughout the course of study participation,
6. Subject is willing and able to refrain from engaging in any non-study procedure therapies for the management of his or her neck/shoulder pain throughout the course of study participation, including conventional therapies such as physical therapy, occupational therapy and hot or cold packs, as well as alternative therapies such as chiropractic care and acupuncture
7. 18 years of age or older
8. Male or female
9. Primary language is English

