### **PRE-PROCEDURE EVALUATIONS**

The pre-procedure evaluation phase directly follows successful study qualification, on the same day.

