### **OUTCOME ASSESSMENTS**

- Visual Analog Scale (VAS) Degree of Pain Rating
- Linear Range of Motion (ROM)

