#### Individual Subject Success Criteria

Individual subject success criteria is defined as a 30% or greater decrease in self-reported VAS pain rating at study endpoint relative to baseline.

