## OUTCOME ASSESSMENTS

## **VISUAL ANALOG SCALE (VAS) DEGREE OF PAIN RATING**

Using the scale below, please mark with a cross (X) a SINGLE SPOT along the 0 to 100 line below that best shows how much **pain you feel in your neck/shoulder** right now. '0' means you feel no pain at all and '100' means you feel the worst pain imaginable. PLEASE MARK ONLY ONE SPOT. DO NOT THINK OF OR WRITE IN A NUMBER."

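### The qualification form shows subjects the VAS entry cut-off beside the line they mark, and the plan does not say which pre-treatment mark is the baseline

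*Combined protocol and SAP*

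**What the plan says.** Item 4 of the Inclusion Criteria sets the entry rule: "Subject's self-reported Degree of Pain rating on the 0-100 VAS pain scale is 50 or greater". In Appendix C, the Study Qualification Evaluation form turns this into a single cell. The cell holds, in order, the criterion "Degree of Pain Self-Rating on the 0-100 Visual Analog Scale (VAS) is 50 or greater", an instruction to the subject beginning "Please mark with an 'X' a single spot along the 0 to 100 line below", the further instruction "DO NOT THINK OF OR WRITE IN A NUMBER", the line, and a field for the measured rating. If any inclusion box stays unchecked, the evaluation ends.

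A second pre-treatment rating comes next. Under Pre-Procedure Evaluations: "The pre-procedure evaluation phase directly follows successful study qualification, on the same day". The outcome assessments there include "Visual Analog Scale (VAS) Degree of Pain Rating". The matching Appendix C form has its own line and prints no cut-off. Its question, for the spot that "best shows how much pain you feel in your neck/shoulder right now", is used again at the study endpoint.

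Under Individual Subject Success Criteria, success is a "30% or greater decrease in self-reported VAS pain rating at study endpoint relative to baseline". The plan does not say in words which of the two marks is the baseline. The Study Design and Blinding sections describe one group, with neither subjects nor investigators blinded. The comparison is with red-diode data from the 2001 study.

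**The concern.** A subject who follows the instruction on the qualification form has the number that decides entry in view, in a cell that also asks the subject not to think of a number. Someone whose pain is a little under 50 has a reason to mark 50 or more.

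This matters because the primary endpoint is a percentage fall from a self-reported starting score. If that score is too high, a later return to the subject's true level counts as relief, and less real improvement is needed to be a responder. With no concurrent control arm, the inflation has nothing within the trial to cancel against. The success criterion rests on a historical 65% with a 5-point margin, so a shift of a few points would be of the same order as the margin.

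**Working it through.** **Inputs from the documents.** The reference trial's active group had 28 of 43 responders, with mean VAS falling by 29.0 points from 60.2 to 31.2 (its Primary Endpoint results). The responder rule is a 30% fall. The margin is 5 points with a 60% floor (Overall Study Success Criteria). Sample size is 43.

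**Plan's own figure.** 28/43 = 65.1%, which reproduces the stated 65%. The sample size is copied from the reference arms, so there is no power figure to reproduce.

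**Inputs that are assumptions.** The documents give neither the size of any inflation (d) nor the share of subjects who inflate. I use d = 2, 5 and 10 points and shares of 25%, 50% and 100%.

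**Single subject.** If true pain is T and the recorded baseline is T + d, the endpoint mark must be at most 0.7(T + d). The true fall needed is T − 0.7(T + d) = 0.3T − 0.7d.
- T = 45 marked as 50: endpoint 35 or less; true fall 10/45 = 22.2%.
- T = 42 marked as 50: endpoint 35 or less; true fall 7/42 = 16.7%.
- T = 50 marked as 55: endpoint 38.5 or less; true fall 11.5/50 = 23.0%.

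**Group.** Take the fall as normal with mean 29.0 from a baseline of 60.2. A 30% fall is 0.3 × 60.2 = 18.06 points. For 65.1% to exceed it, SD = (29.0 − 18.06)/z(28/43) = 28.2 points. With inflation fully carried into the baseline and the endpoint mark unaffected, the responder rate among inflaters is Φ((29.0 − 18.06 + 0.7d)/28.2). The overall rate is share × that value + (1 − share) × 65.1%.

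| Inflation d | 25% inflate | 50% inflate | All inflate |
|---|---|---|---|
| 2 points | 65.6% (+0.5) | 66.0% (+0.9) | 66.9% (+1.8) |
| 5 points | 66.2% (+1.1) | 67.4% (+2.2) | 69.6% (+4.5) |
| 10 points | 67.3% (+2.2) | 69.5% (+4.3) | 73.8% (+8.7) |

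If the pre-procedure mark is the baseline and is itself uninflated, d = 0 and the shift is zero, whatever was marked at qualification.

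**Which cells are plausible.** The printed cut-off gives a motive only to subjects near or below 50. The column in which everyone inflates, applied around a mean of 60.2, is an outer bound. With a quarter inflating, the shift is 0.5 to 2.2 points, less than one subject in 43 (1/43 = 2.3 points).

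**The case against.** The strongest reply is that the qualification mark is only an eligibility check. The pre-procedure VAS is listed as an outcome assessment, sits on another form without the cut-off, and has the wording repeated at endpoint. It is made after the subject has qualified, when there is nothing left to gain by marking high. That no rule re-checks a second mark below 50 also helps: a mark that drops back to true pain removes the inflation. This stands as the natural reading, but the plan does not state it, and the two marks are made in direct succession on the same day. Carry-over is therefore plausible, though nothing in the documents shows it.

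It is also fair to say that the form is otherwise an investigator's checklist, that the cut-off lies above the marking instruction rather than on the line, and that the recruitment texts do not disclose it. The protocol's VAS guidance asks only that the line itself be clear of markings, so the layout does not plainly breach it. What remains is that the instruction in that cell is addressed to the subject.

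A reader might infer that the printed cut-off does inflate the responder rate. The documents do not support that, because the route depends on an unstated baseline or on unproven carry-over.

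A reader might also infer that 5 points of inflation would use up the margin, since in this model a true 55% would read as about 59.9%. That needs every subject to inflate, and it looks only at the 60% floor. The Primary Efficacy Outcome Statistical Evaluation section also requires the lower 90% confidence limit for the difference to clear the margin. With a two-sample Wald interval against 28/43, the lower limit is about −22 points for 26/43 and about −7 for 32/43. The first count to clear −5 is 33/43, at about −4.3. The two success rules differ, so an observed 60% cannot simply be called success.

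Finally, the reference trial also required a VAS of at least 50, but its form is not shown. The same cue could have acted there, or not.

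**Conclusion.** The point holds as a form-layout weakness joined to an undefined baseline. The cut-off is in view where the subject marks, and the plan leaves open which pre-treatment mark enters the primary endpoint. Bias can reach the responder rate by two routes: use of the qualification mark as baseline, or carry-over to the second mark.

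The size is unknown. The modelled range of about +0.5 to +8.7 percentage points rests on a normal distribution for the fall, calibration to the reference trial, full carry-over, and assumed values for the amount and prevalence of inflation. The lower part is more credible, because only some subjects have a motive. The shift is zero if the pre-procedure mark is the baseline and is uninflated. The net effect on the comparison with the reference trial cannot be determined from the documents. The lack of a concurrent control is a separate issue that this change would not resolve.

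**What to change.** 1. Have the subject mark the qualification VAS on a separate sheet carrying only the question and the line. Staff then measure it and record the value and the eligibility check on the investigator's page.
2. State that the cut-off is not to be disclosed to subjects.
3. Add a sentence under Individual Subject Success Criteria saying that baseline is the VAS from the pre-procedure evaluation form, not the qualification mark.

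The cost is one extra form page and one or two sentences of protocol text. A few more candidates may score below the entry level and fail screening.
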